5.7 Drug accountability

Batch numbers and expiry dates for all drugs used in the study will be indicated in a study drugs accountability log. The date, quantity, volunteer number as well as the batch number for every administered drug will be noted in a study drug accountability form. A final count will be made after drug administration to the last volunteer.

5.8 Destruction of Study Drug

Unused drugs will be returned to the pharmacy of HUG for destruction.

6. STUDY ASSESSMENTS

The study flowchart and study plan on pages 12 and 13 and section 2.1 provide a summary of the various procedures, measurements and data collections that will be carried out during the study. The following paragraphs complete section 2.1.

6.1 Urine collection

At each session, urine will be collected for 24 hours before omeprazole intake. The total urinary volume will be recorded, aliquoted and stored at -80°C until analysis. These samples will serve for the targeted and untargeted metabolomics analysis that will be carried out by the Laboratory of Forensic Toxicology and Chemistry at the University Centre of Legal Medicine and the Laboratory of Clinical Pharmacology and Toxicology of Geneva University.

6.2 Plasma collection

Six tubes of 6 ml venous blood sample (6 x 6 ml) will be drawn during the three sessions and collected in EDTA plasma collection tubes⁷⁴ at the same time as the omeprazole is administrated. Plasma will be obtained after centrifugation of blood samples at 2500 rcf for 10 minutes and aliquots will be conserved at -80°C until analysis. These samples will serve for the untargeted metabolomics analysis of direct plasma and liver-derived extracellular vesicles (liver-specific liquid biopsy) that will be performed by the Laboratory of Forensic Toxicology and Chemistry at the University Centre of Legal Medicine and the Laboratory of Clinical Pharmacology and Toxicology of Geneva University. Fluvoxamine and rifampicin will also be quantified in the Laboratory of Clinical Pharmacology and Toxicology using validated methods.

6.2.1 Liver-derived extracellular vesicles preparation and characterization

Liquid biopsy can be defined as an indirect analysis of a specific organ using information (DNA, RNA, protein, metabolites) shaded from the organ to the circulation. This approach is widely used in oncology as a non-invasive diagnostic method for early detection of mutations and cancer biomarkers. These circulating markers are present in extracellular vesicles originated from a specific organ. We recently published a proof-of-concept study evaluating the potential use of liquid biopsies as a valid indicator of liver cytochromes activities.⁷⁵ This study shows a good correlation between liver EVs cytochrome expression levels with patients' cytochrome activity as measured by the Geneva phenotyping cocktail.

Liver specific liquid biopsies will be prepared according to the general recommendations of the International Society for Extracellular Vesicles from plasma samples at each session and following the general flowchart presented in Habtemariam and Guchelaar study⁷⁶. It requires to have a sufficient plasma volume for characterization and analysis⁷⁷. Hence, 36 ml of whole blood will be available in this study at each session from each volunteer, from which 30 will be used for EVs while the rest will be used for direct metabolomic analysis in plasma. A preliminary EVs cleaning and enrichment step will be performed by centrifugation to obtain platelet deprived samples. Specific liver derived EVs will then be isolated through immuno-affinity precipitation using magnetic-bead coupled commercial antibodies directed against hepatocyte specific proteins known to be packaged to the surface of EVs. Anti-ASGR1 antibody coupled to Dynabeads (Thermo Fisher Scientific, Waltham, USA) have already been successfully used for the isolation of liver specific EVs and will be our starting method of choice.⁷⁸ The development of new EVs isolation methods is a rapidly evolving field and other isolation techniques might come under consideration depending on the accomplished progress.^{76,79}

Isolated EVs characterization will be performed using a combination of flow cytometry and electron-microscopy (EM) techniques.^{80,81} Vesicle size and homogeneity of the final preparations will be assessed by transmission electron microscopy (TEM) at the EM platform of the University of Geneva. EVs purity and cell specificity will be followed by flow cytometry using a combination of antibodies directed both against liver EVs membrane surface cargos and undesired components (such as platelet EVs markers). During the method development stages, flow cytometry will be used to follow EVs purity as well as subtype specificity and enrichment efficiency at each step of the isolation procedure comparing enriched fractions versus left-overs. Once the experimental pipeline is entirely defined, flow cytometry will remain the technique of choice for testing the quality of each extract but will be limited to key isolation steps and a selection of highly informative antibodies. Antibodies target will include both general EV markers as well as liver specific surface proteins and frequently encountered protein contaminants (such as markers of EVs of a different origin). It was previously demonstrated that normalization of EVs with respect of their number and proportion of cells of hepatic origin is an important step to account for inter-individual variability in EVs production. A shedding factor was therefore developed based on a pool of 13 mRNA markers that will be measured in our study.⁸²

As with urine and plasma samples, EVs will be submitted to untargeted metabolomics after a sample preparation method adapted from recent protocols.⁷⁷

6.2.2 CYP2C19 mRNA and protein measurements

CYP2C19 expression levels in liver biopsies will be measured using conventional techniques. After extraction of messenger RNA using commercial extraction kits and reverse transcription (iScript™ cDNA Synthesis kit, Bio-Rad Laboratories, Inc.), relative quantification of the resulting cDNA will be performed by RT-PCR using validated TaqMan® Expression probes (ThermoFisher Scientific, Waltham, USA) in a StepOne™ apparatus (ThermoFisher Scientific, Waltham, USA).

6.3 Capillary blood collection

2 hours after omeprazole intake at each session, the capillary blood will be sampled by pricking the fingertip using a conventional lancet. A blood drop of 10 µL will be collected by the medical device HemaXis DB 10. In total, 4 x 10 µL will be collected. After 30 minutes drying time at room temperature, DBS samples will be packed in sealable plastic bags containing a desiccant and stored at -20°C until analysis. The extraction of DBS samples will be performed using an automated system, allowing an online desorption of DBS directly into the HPLC-MS/MS device without sample pretreatment. Finally, the quantification of omeprazole and OH-omeprazole will be performed in order to determine the phenotype of CYP2C19 in the Laboratory of Clinical Pharmacology and Toxicology through a validated analytical method.

7. ADVERSE EVENTS MANAGEMENT

7.1 Definitions

An adverse event (AE) is defined as any adverse change from the subject's baseline condition. An adverse event does not necessarily have a causal relationship with the study treatment. AE monitoring begins when participants receive omeprazole during the second visit (session 1) and continues through subsequent visits, with follow-up phone calls two days after each visit, including a final safety follow-up after the fourth visit.

The Common Terminology Criteria for Adverse Events (CTCAE) displays Grade 1 to 5 with unique clinical description of severity for each AE based on this general guideline:

Grade 1: Mild; asymptomatic or mild symptoms; clinical or diagnostic observations only; intervention not indicated.

Grade 2: Moderate; minimal, local or non-invasive intervention indicated; limiting age-appropriate instrumental Activities of Daily Living (ADL) (i.e. preparing meals, shopping for groceries or clothes...).

Grade 3: Severe or medically significant but not immediately life-threatening; hospitalization or prolongation of hospitalization indicated; disabling; limiting self-care ADL (i.e. bathing, dressing and undressing...).

Grade 4: Life-threatening consequence; urgent intervention indicated.

Grade 5: Death related to AE.

A serious adverse event (SAE) as defined by ICH is any untoward medical occurrence that at any dose meets any of the following conditions:

- Results in death
- Is life-threatening (the subject was at risk of death at the time of the event. It does not refer to an event which hypothetically might have caused death if it was more severe)
- Requires or prolongs hospital stay significantly
- Results in persistent or significant disability/incapacity
- Is a congenital anomaly/birth defect
- Is an important medical event

Important medical events are those that may not be immediately life threatening but are clearly of major clinical relevance. They may jeopardize the subject and may require an intervention to prevent one of the other serious outcomes noted above.

SAEs should be followed until resolution or stabilisation. Participants with ongoing SAEs at study termination (including the final safety follow-up) will be further followed up until recovery or until stabilisation of the disease after termination.

An “unexpected” adverse drug reaction (ADR) is an adverse reaction of which the nature of severity is not consistent with the official product information for drugs used in this study.

The investigator makes a causality assessment of the event to the study drug based on the criteria listed in the ICH E2A guidelines:

Relationship	Description
Definitively	Temporal relationship Improvement after dechallenge* Recurrence after rechallenge (or other proof of drug cause)
Probably	Temporal relationship Improvement after dechallenge No other cause evident
Possibly	Temporal relationship

	Other cause possible
Unlikely	Any assessable reaction that does not fulfil the above conditions
Not related	Causal relationship can be ruled out
*Improvement after dechallenge only taken into consideration if applicable to reaction	

A suspected unexpected serious adverse reaction (SUSAR) is defined as a serious adverse event that is not expected (not described before or known with a lower frequency) and which the causation with the study product is established with an imputability of at least possible.

7.2 Adverse events collection and grading

Drugs used in this study are approved in Switzerland and their security profile is well known. Therefore, AEs of grade ≥ 2 , SAEs and SUSARs are unlikely. If that were to happen, only SAEs that result in death and SUSARs would be reported in the eCRF.

AE monitoring and filling out of the eCRF for each participant begins when they receive omeprazole during the second visit (session 1). This monitoring will continue throughout the two-hour duration of the visit and the same procedure will be followed for the third visit (session 2) and the fourth visit (session 3). To ensure comprehensive safety monitoring, a follow-up phone call will be conducted two days after each visit, including the fourth one (final safety follow-up). This allows for the early detection of any potential AEs related to fluvoxamine and rifampicin, as well as adverse events that may appear after the study. Participants will be encouraged to contact study investigators at any time if they experience an AE, even if it occurs after the study has ended. This is particularly important if the participant feels they need to discontinue the medication during the study or if they require medical assistance.

The eCRF report will document the reasons for notification (e.g. death, life-threatening event), the date of first occurrence, and a description of SAEs/SUSARs. The report will also assess the nature of the SAE (expected or unexpected) and its relationship to the study drug (imputability) to determine if it qualifies as a SUSAR. Additionally, information on any potentially responsible medications will be recorded.

All AEs, SAEs and/or SUSARs will be followed up until the event is resolved. The SAEs that are not reported in the eCRF and AEs of grade ≥ 2 will be recorded in the electronic medical records of HUG for each study subject by the investigator.

7.3 Safety reporting

Reporting of AEs

Only adverse events of special interest (AESI) will be reported by the promotor and/or the investigator to the regional centre of pharmacovigilance of Geneva as it is the case under usual conditions of these drugs.

Reporting of SAEs

Only SAEs resulting in death must be reported immediately and within a maximum of 24 hours to the Sponsor-Investigator of the study and to the CCER within 7 days.

Reporting of SUSARs

A SUSAR needs to be reported to the CCER and to Swissmedic for category B and C studies within 7 days, if the event is fatal, or within 15 days (all other events).

Reporting of safety signals

All suspected new risks and relevant new aspects of known adverse reactions that require safety related measures, i.e. safety signals, must be reported to the Sponsor-Investigator within 24 hours. The Sponsor-Investigator must report the safety signals within 7 days to CCER and Swissmedic in case of a category B or C study.

Reporting of pregnancy

Pregnant participants must immediately be withdrawn from the clinical study. Any pregnancy during the treatment phase of the study and within 30 days after discontinuation of study medication will be reported to the Sponsor-Investigator within 24 hours. The course and outcome of the pregnancy should be followed up carefully, and any abnormal outcome regarding the mother or the child should be documented and reported.

Periodic reporting of safety

An annual safety report (ASR) is submitted once a year to the CCER and to Swissmedic by the Sponsor-Investigator for category B clinical trials.

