Each session includes urine collection over a full 24-hour period that will start in the morning of day 0 for session 1, day 10±4d for session 2 and day 26±4d for session 3. It will end in the morning of day 1 for session 1, day 11±4d for session 2 and day 27±4d for session 3. Since most of this part will be performed at home, subjects will be given precise instructions on how to perform it. The last urine stream for each session will be collected in the morning after an overnight fast. Urine will be collected into a 24-hour collection container. This will be stored in a cooler with ice packs and/or a refrigerator.

Immediately after the 24-hour urine collection, venous blood (6 x 6 ml) will be collected and one 10 mg tablet of omeprazole (Antrumups®) administrated. Women will only receive omeprazole after verifying that they are not pregnant (urine test). 2 hours after omeprazole intake, capillary blood sampling (DBS sampling) will be performed. Volunteers will then be free to leave the HUG. Breakfast will be served after capillary blood sampling.

No wash-out period is necessary between the first and second session as fluvoxamine treatment lasts one week, which is sufficient to eliminate omeprazole administered in the first session, as well as its metabolites. Indeed, omeprazole's half-life elimination is generally less than 1 hour, and does not exceed 3 hours in PMs healthy subjects^{45,46}. However, a minimum of six days is necessary between session 2 and session 3. This time gap is required because of the half-life elimination of fluvoxamine being 19,5 hours on average after multiple intakes⁴⁷⁻⁴⁹.

Concerning the second session, participants will be instructed (orally and through reception of an instruction card) to take one 50 mg tablet of fluvoxamine (Floxyfral® junior) every morning for one week (7 doses in total) with the breakfast. If the third visit (session 2) happens exactly 7 days after the second visit (session 1), the drug must be taken during the lunch of session 1 (day 1) in order to have a total of 7 doses of fluvoxamine administrated. Otherwise, the treatment must start one week before the third visit (session 2) and the last dose must be taken 2 hours before omeprazole intake during the day 1 of session 2.

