Concerning the third session, participants will also be instructed to take two 300 mg tablets of rifampicin (Rimactan®) every evening for 10 days (10 doses in total) before the fourth visit. This regimen will begin at least 6 days after the third visit (session 2) and the last rifampicin intake will be done at the evening preceding the fourth visit (session 3).

Volunteers will be asked to back empty blisters of the drugs that they took home in order to verify compliance.

The total study duration will not exceed 32 days. Therefore, the first dose of fluvoxamine and rifampicin must be taken, at the latest, 9 days and 21 days after day 1 of session 1, respectively (see study design page 13).

The order of sessions is purposely not randomized due to unnecessity. Indeed, as it is solely a PK study performed on paired samples, there are no possible biases requiring randomization.

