Rifampicin acts as a strong inducer of CYP2C8, 2C9, 2C19 as well as 3A4/5 and a weak inducer of CYP1A2 and 2B6.^{17,24,50,64,70,71} Consequently, many concomitantly administered classes of drugs such as benzodiazepines, calcium antagonists, protease inhibitors and neuroleptics become ineffective. This also includes oral contraceptives, which makes barrier contraceptive method an important requirement. Furthermore, induction does not dissipate until 2 weeks after discontinuing rifampicin, reinforcing the need to use a barrier contraceptive method after stopping treatment (i.e. male or female condom, spermicide or diaphragm).^{64,70,72} In this study, at least one barrier contraceptive method will have to be used for all the study duration and for 1 month after the last visit (session 3). During this period, women who usually take oral contraceptives can keep their intake while using a barrier contraceptive method. It is necessary to administer rifampicin for at least 7 days to achieve the onset of full enzymatic induction. Therefore, 10 days will be applied here, which is sufficient to increase the concentration of endogenous CYP2C19 metabolites.⁷²

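### Pregnancies are reportable for 30 days after study medication, but the last planned contact is 3 days after the last rifampicin dose, leaving 27 days to self-report

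*Protocol*

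**What the plan says.** - **Reporting duty.** Section 7.3: "Any pregnancy during the treatment phase of the study and within 30 days after discontinuation of study medication will be reported" to the sponsor-investigator. Course and outcome are to be followed, and a pregnant participant is to be withdrawn at once.
- **Last contact.** Section 7.2: "a follow-up phone call will be conducted two days after each visit, including the fourth one (final safety follow-up". Participants are also encouraged to get in touch at any time, even after the study, but only about an adverse event.
- **Last dose.** Section 3.1: "the last rifampicin intake will be done at the evening preceding the fourth visit (session 3".
- **Contraception.** Sections 4.2, 5.1.3 and 5.6 require a barrier method during the study and for one month after it. Section 5.1.3 explains why: rifampicin makes oral contraceptives ineffective, and "Furthermore, induction does not dissipate until 2 weeks after discontinuing rifampicin". Women may continue oral contraceptives alongside the barrier method.
- **Pregnancy tests.** There is one at inclusion (3.1) and one at each session (5.6). Section 3.1 writes only one dose as conditional on the result: "Women will only receive omeprazole after verifying that they are not pregnant (urine test".
- **Data capture.** The eCRF list in section 8.1.1 has the pregnancy test result at each visit, but no item for a pregnancy that becomes known after visit 4.

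**The concern.** The protocol recognises that hormonal contraception can fail under rifampicin, and it sets both a contraception period and a reporting window that run about a month past the last dose. Its planned contacts stop almost as soon as dosing does. A conception during the course may be too recent for the visit 4 test, and a conception in the following weeks cannot be found by it. The duty to report and follow outcomes would then depend on a volunteer who was never explicitly asked to report a pregnancy. These are healthy volunteers with no personal benefit beyond learning their genotype and phenotype (section 3.3), so a known risk deserves planned follow-up.

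A second, smaller question is what each test controls. Section 3.1 ties the test to omeprazole alone, while sections 5.6 and 7.3 read more broadly.

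**Working it through.** **Inputs.** Section 3.1 puts the end of the urine collections, and so the visits, on "day 1 for session 1, day 11±4d for session 2 and day 27±4d for session 3". Rifampicin is taken "every evening for 10 days (10 doses in total) before the fourth visit", and "This regimen will begin at least 6 days after the third visit (session 2". The call is at visit + 2 days (7.2), the reporting window is 30 days (7.3), and residual induction is 2 weeks (5.1.3).

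**1. The plan's own calendar.** Session 3 falls on days 23 to 31. Counting from day 0 inclusive, 23 + 1 = 24 and 31 + 1 = 32 days. This reproduces the 24 to 32 days in the synopsis.

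**2. Last dose to last contact.** Last rifampicin = session 3 − 1. First rifampicin = session 3 − 10. Call = session 3 + 2. Window end = last rifampicin + 30.

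| Session 3 day | Rifampicin days | Call | Dose to call | Window end | Days after call |
|---|---|---|---|---|---|
| 23 | 13–22 | 25 | 3 | 52 | 27 |
| 27 (nominal) | 17–26 | 29 | 3 | 56 | 27 |
| 31 | 21–30 | 33 | 3 | 60 | 27 |

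The gap does not depend on the schedule chosen: 27/30 = 90% of the window. If the session 3 omeprazole tablet counts as the last study medication, the window ends one day later and 28 days follow the call. Of the 14 days of residual induction, 14 − 3 = 11 follow the call.

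**3. What the visit 4 test can see (nominal schedule).** A conception during the course (days 17 to 26) is 27 − 26 = 1 to 27 − 17 = 10 days old at the test. The documents give no detection threshold. Assume a urine test turns positive 10 to 14 days after conception. The day 27 test then finds conceptions up to day 27 − 10 = 17 or day 27 − 14 = 13, so almost none from the course itself. It does find earlier ones that the session 2 test on day 11 could not.

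**4. What a contact on day 56 could see.** Conceptions during the course would be 56 − 26 = 30 to 56 − 17 = 39 days old. One at the end of residual induction (day 26 + 14 = 40) would be 16 days old. Under the same assumption, only conceptions in the last 10 to 14 days of the window would still be too recent.

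**5. Age of the test before rifampicin.** Gap = (session 3 − 10) − session 2, with session 2 on days 7 to 15.
- Nominal: 17 − 11 = 6 days, which is also the minimum allowed.
- Maximum: (31 − 10) − 7 = 14 days.
- The session 3 test follows 16 to 24 days after the session 2 test (6 + 10 to 14 + 10), after all 10 doses.

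**The case against.** **A reporting duty is not a promise of active follow-up.** A window longer than scheduled contact can work through participants' own reports, and sections 7.2 and 7.4 accept reports after the study. This is fair: the passages do not strictly contradict each other. But the invitation covers adverse events and does not name pregnancy, so even the passive route is not clearly laid down.

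**Uncovered days are not exposed pregnancies.** This stands. Section 5.1.3 gives rifampicin a half-life of about 1 to 2 hours after multiple doses, so a conception well into the 27 days is not a rifampicin-exposed pregnancy. The 11 days of residual induction bear on contraceptive efficacy, which the barrier requirement addresses directly. The 90% measures planned contact, not harm.

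**Two stronger readings are tempting, and the documents do not support them.**
- A reader might infer from section 3.1 that the tests protect only against omeprazole. Section 5.6 tests at every session and section 7.3 withdraws a pregnant participant at once. A positive test at session 1 or 2 therefore also bars the fluvoxamine or rifampicin course that follows. What remains is timing: the session 2 test is 6 to 14 days old at the first rifampicin dose.
- A reader might infer that pregnancies exposed to rifampicin will be missed. The session 3 test can detect a pregnancy that session 2 could not, although only after exposure, and women may report on their own. The supportable word is could.

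**Absence cannot be fully verified.** The flowchart and design figure are not shown and the consent pages were removed. A later check or an instruction to women may appear there. The text, however, describes none and labels the visit 4 call as the final follow-up.

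**Conclusion.** The point holds in a limited form. The protocol sets a 30-day pregnancy window and schedules nothing to learn of pregnancies after its first 3 days. This is true for every permitted visit schedule and needs no outside figure. Pregnancies conceived late in the rifampicin course or in the window could be missed unless the woman volunteers the information. The statement that the visit 4 test finds almost no conceptions from the course rests on the assumed detection range of 10 to 14 days. Neither a count of missed pregnancies nor a claim that the tests leave rifampicin uncontrolled is supported.

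The metabolomic analysis is unaffected. This is a participant safety point that should be corrected because the remedy is small and follows from a window the protocol has already chosen.

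**What to change.** 1. **Sections 7.2 and 7.3:** schedule one phone contact with each woman at the end of the 30-day window to ask about pregnancy. For completers this is nominal day 56 (range 52 to 60), or one day later if the window runs from the last omeprazole tablet. Include withdrawn women, counting from their own last dose; section 5.5 schedules no contact for them.
2. **Section 8.1.1:** add an eCRF field for the answer and, where relevant, the outcome.
3. **Section 7.2:** extend the invitation to contact the site so that it names pregnancy. This also serves conceptions too recent to be known at the call.
4. **Sections 3.1, 5.6 and 7.3:** reconcile the wording on which drug courses each test controls, given that the session 2 test is 6 to 14 days old at the first rifampicin dose and the next test follows all 10 doses. No clinical rule is proposed here; the choice is the sponsor's.

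**Cost:** one short call per woman in a study of 40 volunteers, one eCRF item and a few sentences of text. The last contact for women moves by 27 days, about four weeks. No dose, visit or sample changes.
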